## **11. STATISTICAL METHODS**

### **11.1. Overview**

The statistical methodology below describes the high-level statistical analysis principles as it is foreseen when the study is being planned.

The statistical analysis plan (SAP) will be prepared prior to first subject enter treatment period and any subsequent amendments will be documented, with final amendments completed prior to database lock.

### **11.2. General Statistical Methodology**

The analysis of all endpoints will include all data captured during the study, unless the subject withdraws consent from study participation, regardless of whether study treatment is prematurely discontinued or delayed, and/or irrespective of protocol adherence.

Summary data will be presented in tabular format by treatment groups. Categorical data will be summarized by the number and percentage of subjects in each category. Continuous variables for parametric data will be summarized by descriptive statistics including n, mean, standard deviation, median, minimum value and maximum value (unless stated otherwise) for non-PK data. For PK data, in addition, geometric mean and coefficient of variation (CV%) based on log-transformed data will be presented.

### **11.3. Study Populations**

#### **11.3.1. Safety Analysis Set**

The safety analysis set will include all subjects who received benralizumab.

Unless otherwise stated the safety analysis set will be used for the presentation of all data except for PK data.

#### **11.3.2. Pharmacokinetic Analysis Set**

All subjects who received benralizumab and from whom PK blood samples are assumed not to be affected by factors such as protocol violations (e.g., disallowed medications) and who had at least one quantifiable serum PK observation post first dose will be included in the PK analysis dataset.

### **11.4. Determination of Sample Size**

While this study is not a formal bioequivalence study, a total of 162 subjects (81 subjects per treatment group) are required for this study to achieve with 80% power and a 90% two-sided confidence interval (CI) for geometric mean ratios of AUC and  $C_{max}$  being within a limit of

0.8 to 1.25 inclusive. The calculation is based on two one-sided tests (TOST) at 5% alpha level under an assumption of maximum 50% CV PK variability for primary endpoints of benralizumab AUC and  $C_{max}$ . Assuming 10% dropout rate, 180 subjects will be enrolled to provide adequate numbers of subjects to assess the primary and secondary objectives of the study.

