### Study Rationale

Benralizumab is a humanized anti-eosinophil monoclonal antibody (mAb) and depletes eosinophils via a mechanism of enhanced antibody-dependent cell-mediated cytotoxicity (ADCC). Benralizumab's unique mechanism of action induces direct, rapid and nearly complete depletion of eosinophils in the lung tissue, sputum, blood and bone marrow. Benralizumab has demonstrated pharmacodynamic (PD) activity and clinical efficacy in asthma control in Phase 1, 2 and 3 studies.

In global pivotal trials, benralizumab has been administered by health care providers using accessorized pre-filled syringe (APFS) device. The APFS combination product is a single-use, disposable system that is designed to administer the labeled dose into the subcutaneous (SC) space as 1 injection and automatically provides a safety mechanism to reduce the occurrence of accidental needle-sticks during disposal of the system. The functionality and reliability of APFS for home administration were evaluated in another study (GREGALE). The Autoinjector (AI) combination product is an automated, single-use, disposable system that is designed to administer the labeled dose into the SC space as 1 injection in a two-step operation and has a locking needle shield to reduce the occurrence of accidental needle-sticks during disposal of the system.

An open-label, single dose pharmacokinetic (PK) comparability study is required to demonstrate comparable drug exposure (AUC and  $C_{max}$ ) following SC benralizumab administration by using APFS or AI devices. As for other therapeutic immunoglobulin G (IgG) monoclonal antibodies, body weight was previously identified as a relevant PK covariate for benralizumab. In addition, the use of different anatomical regions for SC injections may influence the absorption of protein drugs. In this study, descriptive comparison of benralizumab PK by weight and injection site will be provided.

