**Determination of Sample Size**

While this study is not a formal bioequivalence study, a total of 162 subjects (81 subjects per treatment group) are required for this study to achieve with 80% power and a 90% 2-sided CI for geometric mean ratios of AUC and  $C_{max}$  being within a limit of 0.8 to 1.25 inclusive. The calculation is based on two one-sided tests (TOST) at 5% alpha level under an assumption of maximum 50% CV PK variability for primary endpoints of benralizumab AUC and  $C_{max}$ . Assuming 10% dropout rate, 180 subjects will be enrolled to provide adequate numbers of subjects to assess the primary and secondary objectives of the study.

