## 5.2. Study Rationale

Benralizumab is a humanized anti-eosinophil mAb and depletes eosinophils via a mechanism of enhanced ADCC. Benralizumab's unique mechanism of action induces direct, rapid and nearly complete depletion of eosinophils in the lung tissue, sputum, blood and bone marrow. Benralizumab has demonstrated pharmacodynamic activity and clinical efficacy in asthma control in Phase 1, 2 and 3 studies.

In global pivotal trials, benralizumab has been administered by health care providers using accessorized pre-filled syringe (APFS) device. The APFS combination product is a single-use, disposable system that is designed to administer the labeled dose into the subcutaneous (SC) space as 1 injection and automatically provides a safety mechanism to reduce the occurrence of accidental needle-sticks during disposal of the system. The functionality and reliability of APFS for home administration were evaluated in another study (GREGALE). The Autoinjector (AI) combination product is an automated, single-use, disposable system that is designed to administer the labeled dose into the SC space as 1 injection in a two-step operation and has a locking needle shield to reduce the occurrence of accidental needle-sticks during disposal of the system.

An open-label, single dose PK comparability study is required to demonstrate comparable drug exposure (AUC and Cmax) following SC benralizumab administration by using APFS or AI devices. As for other therapeutic immunoglobulin G (IgG) monoclonal antibodies, body weight was previously identified as a relevant PK covariate for benralizumab. In addition, the use of different anatomical regions for SC injections may influence the absorption of protein drugs. In this study, descriptive comparison of benralizumab PK by weight and injection site will be provided.

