### 11.9.4. Statistical Analysis of Pharmacokinetic Data

#### 11.9.4.1. Primary PK Analysis Method

The study primary objective is to compare AUC and  $C_{max}$  between APFS and AI devices following a single SC administration of benralizumab.

The analysis of variance (ANOVA) model will be employed on the log-transformed  $C_{max}$  and AUC separately, with fixed effects of treatment (device), body weight group and injection site in order to provide a descriptive comparison of the PK exposure between the 2 devices. The estimated treatment (device) differences and the 90% CI (2-sided) on the log scale will be back-transformed to obtain the geometric mean ratios of AI to APFS and its corresponding 90% CI.

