4. STATISTICAL BASIS FOR SAMPLE SIZE

While this study is not a formal bioequivalence study, a total of 162 subjects (81 subjects per group) are required for this study to achieve with 80% power and a 90% two-sided confidence interval (CI) for geometric mean ratios of area under the concentration-time curve (AUC) and maximum observed concentration (C_{max}) being within a limit of 0.8 to 1.25 inclusive. The calculation is based on two one-sided tests (TOST) at 5% alpha level under an assumption of maximum 50% coefficient of variation (CV) PK variability for primary endpoints of benralizumab AUC and C_{max} . Assuming 10% dropout rate, approximately 180 subjects will be enrolled to provide adequate numbers of subjects to assess the primary and secondary objectives of the study.

5. **RANDOMIZATION**

A total of 180 subjects will be randomized. Subjects will be stratified by body weight category (55.0-69.9 kg/70.0-84.9 kg/85.0-100.0 kg). Within each of the 3 weight groups, subjects will be randomized 1:1:1:1:11 to one of the 6 combinations of treatment (APFS or AI) with injection site (upper arm, abdomen or thigh). As a result, 10 subjects will be allocated to each of the 18 randomization combinations for 2 device groups (Table 1). Randomization lists will be prepared for each study site separately. Randomization numbers will be assigned to subjects sequentially within each weight category at each site. To keep the balance, each site must ensure they randomize subjects in complete blocks.

Once a randomization number has been allocated to a subject, it should not be assigned to another subject.

Day -1 body weight assessment will be used to categorize the body weight groups.

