6.3.9.3 Statistical Analysis of Pharmacokinetic Data

Primary PK analysis

The primary objective is to compare AUC_{inf}, AUC_{last} and C_{max} between APFS and AI devices following single SC administration of benralizumab. The analysis of variance (ANOVA) model will be employed on the log-transformed AUC_{inf}, AUC_{last} and C_{max}, separately, with fixed effects of treatment (device), body weight group and injection site in order to provide a descriptive comparison of the PK exposure between the 2 devices.

The estimated treatment (device) differences and the 90% CI (2-sided) on the log scale will be back-transformed to obtain the geometric mean ratios of AI to APFS and its corresponding 90% CI. The tables will also include the geometric least square means with 95% CI [Table 14.2.3.1]. Supporting statistical output for the analysis of PK parameters documented in Appendix 16.1.9.2.1.

The following SAS code will be applied, with AI sorted before APFS:

proc mixed data = <data>;

class <treatment_device> <weight category> <injection site>;

model <log_var> = <treatment_device> <weight category> <injection site>;

lsmeans <treatment_device> / cl alpha = 0.05;

```
estimate "AI versus APFS" <treatment_device> 1 -1 / cl alpha = 0.10;
```

run;

quit;

Secondary PK analysis

For T_{max} , a nonparametric analysis may be performed, based on evaluation during the blind data review.

To evaluate the PK of benralizumab administered to various anatomical injection sites and weight category, the PK parameters will be summarized by treatment (device) and injection sites [Table 14.2.2.3], and body weight categories [Table 14.2.2.2].

Furthermore, the ANOVA model of the primary analysis with the addition of the interaction term treatment (device)-by-injection site will be presented [Table 14.2.3.2]. The estimated differences of pairwise comparison between injection site within each treatment (device) and the corresponding 90% CI (2-sided) on the log scale will be back-transformed to obtain the geometric mean ratios of abdomen/arm, thigh/arm and thigh/abdomen and their corresponding 90% CIs.

Supporting statistical output for the analysis of PK parameters documented in Appendix 16.1.9.2.2.

The following SAS code will be applied:

proc mixed data = <data>;

class <treatment_device> <weight category> <injection site>;

model <log_var> = <treatment_device> <weight category> <injection site>
 <treatment_device> * <injection site>;

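### Is the 80% power statement unsound because it omits the assumed true ratio and a rule for a split AUC/Cmax result?

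*Protocol*

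**What the plan says.** Protocol 11.4, repeated in the synopsis and in SAP 4, states that "a total of 162 subjects (81 subjects per treatment group) are required for this study to achieve with 80% power". The criterion is a 90% two-sided interval for the AUC and Cmax geometric mean ratios lying within 0.8 to 1.25. The method is two one-sided tests at 5%, "under an assumption of maximum 50% CV PK variability for primary endpoints of benralizumab AUC and" Cmax. A 10% dropout allowance takes 162 to 180. The same paragraph opens by saying that the study is not a formal bioequivalence study.

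The rationale (synopsis and Protocol 5.2) uses stronger language: "An open-label, single dose PK comparability study is required to demonstrate comparable drug exposure (AUC and" Cmax). The stated primary objective, in Protocol 6.1 and SAP 1.1, is only to compare exposure between the devices.

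Protocol 11.9.4.1 fits an ANOVA to log Cmax and log AUC separately, "in order to provide a descriptive comparison of the PK exposure between the 2 devices", and reports AI/APFS ratios with 90% intervals. SAP 6.3.9.3 uses the same model and the same descriptive purpose, but with three parameters: "The primary objective is to compare AUC_{inf}, AUC_{last} and C_{max} between APFS and AI devices". Neither analysis section mentions 0.8 to 1.25.

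**The concern.** A sample size for two one-sided tests depends on the true ratio as well as on the CV, the limits and alpha. Without that ratio, 162 cannot be derived from what is written, and a reader cannot see how quickly the 80% erodes if the devices differ slightly.

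The phrase about AUC and Cmax lying within the limits can also mean each of them or both of them. The two readings have different power unless the parameters are almost perfectly correlated.

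The rationale speaks of demonstrating comparable exposure, yet the limits appear only in the sizing text. If one interval fell inside them and another outside, the documents would not say whether comparability had been shown, and that could be settled after the results were known. The SAP adds to the doubt: its Section 4 sizes for an unspecified AUC, while its Section 6.3.9.3 analyses two.

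**Working it through.** **Inputs.** From Protocol 11.4: 81 per device, limits 0.80 and 1.25, 5% per one-sided test, CV at most 50%, dropout 10%. From Protocol 8.9.2: 18 equal randomization cells. Not stated, so varied here as assumptions: the true ratio and the AUC–Cmax correlation.

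**1. Interval width.**
- Log-scale SD = sqrt(ln(1 + 0.5²)) = sqrt(ln 1.25) = 0.4724.
- Standard error of the log ratio = 0.4724 × sqrt(2/81) = 0.0742.
- With t(0.95, 160 df) = 1.654, the half-width of the 90% interval is 1.654 × 0.0742 = 0.1228.
- ln 1.25 = 0.2231, so the estimated log ratio must lie within ±(0.2231 − 0.1228) = ±0.1003, which is 1.352 standard errors.

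**2. The plan's figure at a true ratio of 1.00.** Taking the SD as known gives 2Φ(1.352) − 1 = 82.4%. Integrating over the sampling distribution of the SD gives 82.3%. The smallest size that reaches 80% is 78 per device (80.4%; 77 gives 79.7%), or 156 in total. Spread over 18 equal cells, 156/18 = 8.67, which rounds up to 9, and 9 × 18 = 162. A true ratio of 1.024 also gives exactly 81 per device. The documents do not show which route was used. The dropout step reproduces: 162/0.9 = 180.

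**3. Dependence on the true ratio, 81 per device, each parameter singly.**

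| True ratio | CV | Power |
|---|---|---|
| 1.00 | 50% | 82.3% |
| 0.98 | 50% | 80.7% |
| 0.976 or 1.024 | 50% | about 80% |
| 1.05 | 50% | 73.4% |
| 0.95 | 50% | 72.5% |
| 0.95 | 45% | 80.5% |
| 0.95 | 40% | 87.9% |

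The shortfall at 0.95 belongs to CVs near the plan's ceiling. If all 180 subjects are evaluable, power at ratio 1.00 and CV 50% is 86.9%.

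**4. If both AUC and Cmax had to be inside (ratio 1.00, CV 50%, 81 per device).** At zero correlation, power is 0.8225² = 67.7%; at perfect correlation it is 82.3%. Simulation gives 72.5%, 74.2% and 78.2% at correlations of 0.7, 0.8 and 0.95. The chance that exactly one is inside is 2 × (single − joint). At 0.8 that is 2 × (82.3 − 74.2), about 16%; at 0.7 it is about 19%; at 0.95 about 8%. With 90 per device the joint figure is 79.3% to 83.8% for correlations of 0.7 to 0.95. All these correlations are assumed.

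**5. Which AUC.** The 50% ceiling is set for AUC without distinction. The calculation in steps 1 to 3 is therefore the same for AUCinf and AUClast.

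**6. What the plan does with the intervals.** Each parameter has its own ANOVA, its own ratio and its own 90% interval. There is no combined endpoint, no joint test and no pass or fail statement. A split result would appear as separate ratios and intervals, each of which the reader can set against 0.8 to 1.25.

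**The case for a change.** The best case for a change is that the plan sizes for a criterion, states an aim of demonstrating comparability, and then never says how the criterion will be read. Calling the study not a formal bioequivalence trial does not fully answer this, because the same sentence adopts bioequivalence limits and a power target. At the maximum CV a split result is not rare (about 16% at an assumed correlation of 0.8). Reading rules should be fixed before the data are seen. The SAP's step from one AUC to two is also absent from its list of changes from the protocol (SAP 6.3.12). Repair would cost a few sentences.

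Part of this stands. The true ratio and the basis of the 80% are unreported assumptions, and a reader cannot reproduce 162 without supplying a ratio.

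The rest carries less weight. The word demonstrate occurs in the rationale, whereas the objective and the analysis sections speak of comparing and describing. In a descriptive comparison two differing intervals are reported as they are and need no tie-break. The three-parameter list is the detail a SAP exists to supply, and both AUCs are analysed and reported, so neither can be dropped unseen. Joint-power figures would need correlations that the documents do not give, and writing them into the protocol would add unsupported numbers.

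**Conclusion.** This is missing detail, not an inconsistency. No two passages disagree on sample size, CV, limits, alpha or dropout. Read per parameter, the claim holds with a small margin: 82.3% against the stated 80% at a true ratio of 1.00 and a CV of 50%, and about 80% or more for ratios from 0.976 to 1.024. That range shows what 162 is compatible with; it does not show what the sponsor assumed. The per-parameter reading fits the separate models, although fitting separately does not by itself settle what the 80% refers to.

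The exposed case is a true ratio near 0.95 with the CV at its ceiling, where power is 72.5%. It recovers to 80.5% at a CV of 45%. Followed as written, the plan yields the same estimates and 90% intervals whichever reading is taken, and an analyst needs no further instruction to produce them. Stating the ratio would improve the record but would alter neither enrolment, model nor results, so no change is called for. This conclusion rests on the comparison staying descriptive, as Protocol 11.9.4.1 and SAP 6.3.9.3 say.

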### 11.5. Protocol Deviations

Protocol deviations are considered any deviation from the clinical study protocol relating to a subject. All protocol deviations will be discussed at the data review meeting prior to database hard lock in order to define the analysis sets for the study and all important protocol deviations will be listed by subject.

### 11.6. Subject Disposition

Subjects and/or data excluded from the PK analysis set will be listed including the reason for exclusion. Summary tabulation of subject disposition will be provided. A listing of informed consent response and a randomization listing will also be presented.

### 11.7. Demographic and Baseline Data

Demographic variables (age, gender, race, ethnicity, height, weight and BMI) will be listed by subject and summarized. Listing of medical history will also be provided.

### 11.8. Prior and Concomitant Medication and Drug Administration

Prior and concomitant medication will be listed and drug administration dates and times will be listed for each subject.

### 11.9. Pharmacokinetic Analysis

#### 11.9.1. Pharmacokinetic Parameters

Where possible, the following PK parameters will be assessed for benralizumab on serum concentrations.

#### Primary Pharmacokinetic Parameters

AUC	Area under the concentration-time curve
$C_{max}$	Maximum observed concentration

## Secondary Pharmacokinetic Parameters

$T_{max}$	Time when the maximum concentration is observed
$t_{1/2}$	Terminal half-life
CL/F	Apparent extravascular clearance
$V_z/F$	Apparent volume of distribution based on the terminal phase

Additional PK parameters may be determined where appropriate.

### 11.9.2. Derivation of Pharmacokinetic Parameters

The non-compartmental analysis (NCA) of the serum concentration data for benralizumab will be performed by PAREXEL Quantitative Clinical Development (QCD) using Phoenix WinNonlin (version 6.3 or higher) in accordance to PAREXEL SOPs.

Pharmacokinetic analysis will, where possible, be carried out using actual times recorded in the raw data. If actual times are missing, nominal times will be used. Serum concentration data associated with positive ADA status may be excluded from the NCA.

### 11.9.3. Presentation of Pharmacokinetic Data

A listing of PK blood sample collection times, as well as derived sampling time deviations will be provided. Serum concentrations and PK parameters will be summarized using appropriate descriptive statistics. Figures showing individual and mean of PK concentration-time profiles will be produced on both semi-log and linear scales. Serum concentration data associated with positive ADA status will be flagged in the PK concentration listings and may be excluded from the summary statistics and/or mean profiles.

### 11.9.4. Statistical Analysis of Pharmacokinetic Data

#### 11.9.4.1. Primary PK Analysis Method

The study primary objective is to compare AUC and  $C_{max}$  between APFS and AI devices following a single SC administration of benralizumab.

The analysis of variance (ANOVA) model will be employed on the log-transformed  $C_{max}$  and AUC separately, with fixed effects of treatment (device), body weight group and injection site in order to provide a descriptive comparison of the PK exposure between the 2 devices. The estimated treatment (device) differences and the 90% CI (2-sided) on the log scale will be back-transformed to obtain the geometric mean ratios of AI to APFS and its corresponding 90% CI.

#### **11.9.4.2. Secondary PK Analysis Method**

For  $T_{max}$ , a nonparametric analysis may be performed. Secondary PK parameters will be summarized.

To evaluate the PK of benralizumab administered to various anatomical injection sites, the PK parameters will be summarized by injection sites, body weight ranges and treatment (device). Furthermore, a similar ANOVA model for primary analysis may be used to include the interaction of treatment (device)-by-injection site.

### **11.10. Analysis of Safety Data**

#### **11.10.1. Adverse Events**

Adverse events will be summarized by means of counts summaries by study period (pre-treatment and treatment period). Adverse events will be listed for each subject and summarized by System Organ Class (SOC) and Preferred Term assigned to the event by Medical Dictionary for Regulatory Activities (MedDRA).

Other safety variables will be summarized as appropriate. Further details will be provided in the SAP.

#### **11.10.2. Vital Signs**

The results of the vital signs measurements will be listed and summarized.

#### **11.10.3. Resting 12-Lead Electrocardiogram**

Twelve-Lead ECG results will be listed for each subject.

